Inclusion criteria card recipients: (1) VASDHS Veteran with an active high-risk flag, (2) 18 years of age or older, and (3) decisional capacity. *Exclusion criteria for card makers and recipients:* (1) the absence of a mailing address, working phone number, and email address, (2) inability to read and write in English, (3) previous or current experience as either card maker or recipient, and (4) currently employed by the VA San Diego. If COVID-19 precautions are in effect, Veterans will also be screened for access to reliable computer, tablet, or smartphone with camera and internet access, as well as the willingness to participate in this study remotely. Participants' decisional capacity for informed consent in order to meet eligibility for this study will be assessed during consent (separate from screening call) via the University of California San Diego Brief Assessment of Capacity to Consent (UBACC) will be collected by the study coordinator.

Given that we will likely be conducting at least some of our groups via telehealth, we would like to amend our inclusion criteria for card makers by distinguishing between in person groups vs. telehealth groups for criterion #3, which will be amended to (3) access to transportation to attend the group (if being held in person).

We would also like to amend our exclusion criteria for card makers by adding (5) if participating in group via telehealth, the absence of access to reliable computer, tablet, or smartphone with camera and internet access.

Enrollment- Consent and Baseline Assessment: Following the screening procedures outlined above, Veterans will be invited to participate as either a card maker or recipient (depending on their HRF status). Consent and baseline assessments will be completed either via phone, VA Video Connect (VVC), WebEx, or in-person. If consent is obtained via phone or VVC, or WebEx, we will adhere to current approved guidelines (i.e., use My Health-e-Vet, using MS Azure, have Veteran send signed consent form via email, have Veterans fax, or have the study coordinator take a screen shot of the signed consent during their VVC or WebEx session).

Following consent, Veterans will complete a baseline assessment battery that consists of the following questionnaires: Beck Scale for Suicidal Ideation (BSS), Columbia-Suicide Severity Rating Scale (C-SSRS), Interpersonal Needs Questionnaire (INQ-15), and NIH Toolbox Adult Social Relationship Scales.

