If a Veteran is conservated, the study coordinator will obtain their conservator's consent for study enrollment, as well as the assent of the conserved Veteran.

Caring Cards Groups (Veteran card makers with inactive HRFs): Our study will include three groups, each with 10 Veterans; they will meet separately for 120 minutes once per week at the VASDHS for six months. If groups are unable to take place in-person due to COVID-19 precautions, groups will take place using the VA-approved virtual platform, WebEx. Groups will be facilitated by a post-doctoral or intern-level therapist supervised by the PI, who is a licensed clinical psychologist. If groups are unable to meet in-person, art supplies and cards will be mailed to the group members at their mailing address. If groups take place remotely, this may increase recruitment; however, due to the scope of this pilot project, enrollment will be capped at 10 Veterans per group (a total of 30 card makers). Group members will be assessed for suicide risk at enrollment and follow-up. In addition, the groups' facilitator will remind Veterans at the start of each group to please let them know before the end of group if they are experiencing any thoughts of suicide or homicide. If group is conducted virtually, the Veteran may ask the facilitator to call them after the group has concluded. If suicide is reported, the group's facilitator will further assess their risk by completing a C-SSRS; if the Veteran's C-SSRS is positive, the facilitator will contact the PI for further risk assessment and Safety Planning.

Sending Caring Cards (Veteran card recipients with active HRFs): A total of six cards, one per month, for six months will be mailed. Veterans recruited from psychiatric inpatient care will be mailed a card within the week following their discharge; cards will be sent on a monthly basis thereafter. This is consistent with post-discharge caring contacts recommendations. The study coordinator will contact Veterans via phone two weeks after the card was sent to confirm they received it. Because card-recipients are receiving regular contact by VA Suicide Prevention Coordinators and will receive formal suicide risk assessment at enrollment and follow-up, they will not be directly assessed for suicide risk following the mailing of each card.

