Monitoring of Suicidal Ideation: This is a challenging aspect the study and so we have developed our procedures to be consistent with the recommendations of organizations such as NIH in clinical research in people with elevated suicide risk (e.g., Issues to Consider in Intervention Research with Persons at High Risk for Suicidality). We will further refine our procedures by use of deployment focused discussions with stakeholders in the study start up phase and in collaboration with the Data Safety Monitoring board. The referral sources for this study are VASDHS' Veterans with inactive and active high-risk suicide flags. Veterans with active high-risk suicide flags are closely monitored and regularly assessed for suicide risk by the VASDHS' Suicide Prevention Coordinator (SPCs). At baseline, participants are administered the C-SSRS55. Veterans are informed during consenting that all suicidal behavior is documented in Suicide Behavior Reports in CPRS if not already entered. If ideation exceeds a score of 2, the PI will be contacted and will perform a telephone evaluation and refer the screened potential participant to the SPCs or emergency services as necessary. Our safety monitoring guide details these procedures, how they are recorded, and what the staff, facility, and investigator responsibilities are. All Veterans are provided the contact information for the Veterans' Crisis Line. Any new suicidal behavior will be documented in the Suicide Behavior and Overdose Report in CPRS by research staff. Participants who elect to withdraw from the study will continue to receive suicide prevention services per VA San Diego's protocol. We will monitor these protocols during the course of the study and will make adjustments to inclusion/exclusion criteria or safety protocol in case of adverse events.

All research personnel will complete VA TMS trainings pertinent to suicide prevention.

Confidentiality: In order to protect confidentiality, all participant data will be de-identified by

assigning each participant a unique ID in computer files, and all physical files from the study will be kept in a locked cabinet in study offices at the Veterans Medical Research Foundation building in San Diego. All electronic data and files will be stored on a secure server. Only study investigators and personnel will have access to these data. All documentation will identify participants only by their Unique ID number and not other personally identifying information.

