If COVID-19 precautions are in effect, Veterans will also be screened for access to reliable computer, tablet, or smartphone with camera and internet access, as well as the willingness to participate in this study remotely. Participants' decisional capacity for informed consent in order to meet eligibility for this study will be assessed during consent (separate from screening call) via the University of California San Diego Brief Assessment of Capacity to Consent (UBACC) will be collected by the study coordinator.

Section 10.2 Pregnant Women

10.2a) Are pregnant women the focus of the research?

Yes No

10.2b) Provide the justification for including pregnant women and address any special risks, protections, and safeguards.

Being pregnant is not an exclusion criterion for this study; they are not an explicit focus of this research. There are no risks associated with this study that would apply specifically to pregnant women.

Section 11 - Recruitment

11) Describe, step-by-step, the plans for recruitment of subjects (or selection of subjects as in record review). This description must include how, when, and where potential subjects are approached as well as procedures for identifying potential participants (through medical records, physician referral, third-party sources, etc.). Include how selection is equitable. Indicate if vulnerability to coercion may be present and if so plans to ensure voluntary participation.

Recruitment: The VASDHS keeps record of all Veterans with inactive and active HRFs. A waiver of HIPAA authorization will be obtained in order to extract CPRS contact information (i.e., mailing address and telephone number) of Veterans with inactive and active HRFs. A letter to prospective participants introducing the study (see letter attached to protocol submission) will be sent. Letters to Veterans with inactive HRFs will be sent by the Chief of Psychology, [name], who is a co-I of this project. Letters sent to Veterans with active HRFs will be sent by their Suicide Prevention Coordinators who are in regular contact with HRF Veterans (via phone and mail). Per standard protocol, two weeks after the letter is sent, the study coordinator will contact the prospective participants by phone.

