research project, or for other research for which the use or disclosure of protected health information would be permitted by the Privacy Rule. **38 U.S.C. 7332 Information:** If the waiver of HIPAA authorization is for the use of 38 USC 7332 information (applicable to drug abuse, alcohol abuse, HIV infection, and sickle cell anemia records), by signing this protocol for submission the PI is providing written assurance that the purpose of the data is to conduct scientific research and that no personnel involved may identify, directly or indirectly, any individual patient or subject in any report of such research or otherwise disclose patient or subject identities in any manner. (Ref: 38 U.S.C. 7332(b)(2)(B))

Agree Disagree

12.10f) The research could not practicably be conducted without the waiver or alteration.

Agree Disagree

12.10f2) Describe how the waiver/alteration enables the research to be conducted

The waiver is essential is for screening subjects and having access to CPRS to collect and use the names, telephone numbers, mailing address, as well as CPRS medical records (notes) as they apply to the inclusion/exclusion criteria (see 12.10a for details on what information will be collected during the telephone screens).

12.10g) The research could not practicably be conducted without access to and use of the PHI.

Agree Disagree

12.10g2) Describe why it would be impracticable to conduct this research without the PHI described 12.10a. (v3 /8/18)

Access to and use of the PHI is critical to identifying eligible participants, sending them an introductory letter to the study, and conducting a telephone screen thereafter. The present study depends entirely on access to this PHI and could not be completed without it.

Section 13 - Alternatives to Participation

13) Describe the alternatives to participation in this research study (see ? for guidance)

The alternative to participation is to not participate. Veterans with inactive HRFs may participate in other VASDHS mental health groups; Veterans with active HRFs may continue receiving regular outreach by VASDHS' Suicide Prevention Coordinators (e.g., phone calls).

Section 14 - Potential Risks

14) Describe any potential or known risks or discomforts and assess their likelihood and seriousness (see ? for guidance)

There are minimal risks to participating in the Caring Cards group, meet-up groups (optional), or receiving cards.

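### Card recipients are exempt from risk assessment after each card on the strength of Suicide Prevention Coordinator contact that is described for active flags, but flag status is not re-checked after entry; the existing receipt call could carry a short risk reminder

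*Protocol*

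**What the plan says.** Section 9, Sending Caring Cards, states the rule for recipients: "they will not be directly assessed for suicide risk following the mailing of each card". The same sentence of the protocol opens with two reasons for it: "Because card-recipients are receiving regular contact by VA Suicide Prevention Coordinators and will receive formal suicide risk assessment at enrollment and follow-up". The rule covers all recipients for the whole card period of six monthly cards. That paragraph also sets one study contact: "The study coordinator will contact Veterans via phone two weeks after the card was sent to confirm they received it".

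An active flag is how recipients qualify ("VASDHS Veteran with an active high-risk flag"). Sections 9, 10 and 12.10 all treat it as an entry criterion. Section 27.4 lists presence of a flag among the database fields but gives no schedule for updating it.

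Suicide Prevention Coordinator contact is described by flag status in several places:

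- Sections 9.9 and 15: "Veterans with active high-risk suicide flags are closely monitored and regularly assessed for suicide risk".
- Section 11: "Letters sent to Veterans with active HRFs will be sent by their Suicide Prevention Coordinators who are in regular contact with HRF Veterans". Letters to inactive-flag Veterans come from the Chief of Psychology instead.
- Section 13: "Veterans with active HRFs may continue receiving regular outreach by" the site's Suicide Prevention Coordinators. The option named there for inactive-flag Veterans is other mental health groups.

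Card makers have inactive flags. For them, Section 9 (Caring Cards Groups) says that the "facilitator will remind Veterans at the start of each group to please let them know before the end of group" of any suicidal or homicidal thoughts. A report leads to a C-SSRS and, if that is positive, to the PI.

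**The concern.** Formal assessment at enrolment and follow-up says nothing about the months between them, so in that period the rule depends on Suicide Prevention Coordinator contact alone. The protocol ties that contact to a status that it verifies once and that can change; the card-maker cohort consists of Veterans whose flags are no longer active. No section says what happens if a recipient's flag lapses during the card period.

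Section 14 names worsening ideation during the intervention as a risk, along with discomfort from cards that recall the recipient's own difficulties. If coordinator contact falls away for a recipient with a lapsed flag, a rise in ideation reaches the study before follow-up only if that person volunteers it or attends a meet-up. Such a recipient then has the same flag status as a card maker but fewer scheduled prompts.

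**Working it through.** The plan gives no figure to reproduce. The check is a comparison of sections plus interval arithmetic.

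**Inputs**

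- 50 recipients; six cards, one a month (Section 9).
- Receipt call two weeks after a card is sent (Section 9). One call per card is assumed; the feasibility measure, the ratio of cards sent to cards received, implies it.
- Follow-up within one month after delivery of the last card (Section 9, Follow-up Assessments).
- Four meet-ups over the study's duration (Section 9), or one to four in the 12.15.21 amendment. Section 4 estimates the study at two years.

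**Length of the interval.** Put the first card at month 0 and assume prompt delivery. Cards go out at months 0, 1, 2, 3, 4 and 5, so follow-up falls between month 5 and month 5 + 1 = 6. The interval from baseline is longer by the delay to the first card, which is not stated.

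**Scheduled study contacts in that interval**

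| Contact | Timing | Risk prompt stated? |
|---|---|---|
| Formal assessment | None between enrolment and follow-up | Not applicable |
| Receipt call | Months 0.5, 1.5, 2.5, 3.5, 4.5, 5.5 (the last may fall after follow-up) | No; it confirms delivery |
| Meet-up | One to four over the whole study, optional | Yes, for those who attend |

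The meet-ups are spread over the study, so they need not fall within a given recipient's card period. The documents do not allow a count of meet-up prompts per recipient.

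**If a flag lapses (assumed times)**

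| Lapse at month | Time to follow-up | Receipt calls left |
|---|---|---|
| 1 | 5 − 1 = 4 to 6 − 1 = 5 months | 1.5, 2.5, 3.5, 4.5, (5.5): 4 to 5 |
| 3 | 5 − 3 = 2 to 6 − 3 = 3 months | 3.5, 4.5, (5.5): 2 to 3 |
| 5 | 5 − 5 = 0 to 6 − 5 = 1 month | (5.5): 0 to 1 |

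Meet-ups aside, the middle column is the time without a scheduled study prompt. With a reminder on each call, the longest wait after the first call is about 1.0 month, from one call to the next. After the month-4.5 call, the wait to follow-up or the last call, whichever comes first, is 0.5 to 1.0 month.

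**Number affected.** No lapse rate is given. If 0%, 10% or 50% of 50 recipients lapsed, that would be 0, 5 or 25 people. These are assumptions that show the range.

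**Volume of the fix.** 50 × 6 = 300 calls at most. If the last call falls after follow-up, 50 × 5 = 250 of them come before it.

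**The case against.** The strongest reply is that harm needs two facts that the protocol does not state: that recipients' flags lapse within about six months, and that Suicide Prevention Coordinator contact then declines. The rule itself ascribes the contact to recipients as a class, and no section says it ends when a flag is inactivated. This stands, and it limits the point to a conditional gap.

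A reader might infer that recipients whose flags lapse go unmonitored until follow-up. The documents do not support that. Meet-ups are open to all participants and carry a risk reminder with the same escalation. Section 15 sets a response, whatever the flag, once imminent risk is determined or an unrecorded attempt is disclosed, and all Veterans receive Crisis Line details. Sections 9.9 and 15 also promise refinement with stakeholders and the Data Safety Monitoring board, adjustment after adverse events, and a safety monitoring guide that is not shown.

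These safeguards narrow the gap without closing it. Meet-ups are optional and few. The Section 15 response starts once risk is known; its adverse-reaction trigger names screening, assessments and groups but not receipt calls, and its item triggers come from instruments given at baseline and follow-up. The Crisis Line depends on the recipient acting.

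It is also fair to say that a group reminder differs from a telephone reminder, that either relies on disclosure, and that an inactive flag suggests lower current risk. For that reason no ratio of card-maker to recipient prompts is used here. What remains is that the protocol itself thought a recurring reminder worthwhile for inactive-flag card makers.

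**Conclusion.** The point holds as a modest, conditional safety gap. A rule fixed for the whole card period rests, between the two formal assessments, on contact described for active flags, and flag status is not re-checked after entry. A recipient whose flag lapses, and whose coordinator contact then lessens, could go up to about 4 to 5 months (lapse at month 1) with no scheduled study risk prompt outside the optional meet-ups.

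This assumes prompt monthly cards and one receipt call per card. The lapse rate and the loss of contact are both inferred, so the number affected could be zero. The documents do not show that the rule contradicts another section, that any recipient will lose contact, or that the study lacks a safety response. The change is worth making because the possible consequence is serious and the remedy uses calls already planned. Confidence is medium.

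**What to change.** In Section 9, Sending Caring Cards, add to each two-week receipt call, for all recipients whatever their flag status, the reminder that card makers already receive: tell the caller about any suicidal or homicidal thoughts. If thoughts are reported, the study coordinator completes a C-SSRS and, if it is positive, contacts the PI for fuller risk evaluation and safety planning. The coordinator already collects the follow-up C-SSRS, and Section 15 provides C-SSRS training for study personnel. The statement that recipients are not formally assessed after each card can otherwise stay.

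Giving the reminder to everyone is better than re-checking flags and prompting only those that have lapsed. That route would need up to 50 × 6 = 300 chart look-ups. It would also raise the question of whether the signed HIPAA Authorization covers them, since the waiver in Section 12.10 is for screening. And it would make study contact depend on a post-baseline event related to the Aim 3 outcome.

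The cost is one sentence on up to 300 existing calls, an occasional C-SSRS, a wording amendment, and a small uniform change in contact content to be noted when the recipients' pre/post change in suicide risk (Aim 3) is reported. No new contact or staff is needed.

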Aim 1: Establish the feasibility and acceptability of Caring Cards for Veteran card makers and recipients (i.e., 70% average group attendance, > 75% average satisfaction with group participation and card receipt, and 70% average follow-up response). Establish feasibility and acceptability for optional meetup groups (i.e., 70% average meetup group attendance [feasibility] and > 75% average satisfaction with meetup groups [acceptability]).

Aim 2: Evaluate pre/post changes in thwarted belongingness and perceived burdensomeness among card-makers and recipients.

Aim 3: Evaluate pre/post changes in social connectedness and suicide risk among card makers and recipients.

Section 7 - Background and Significance

7) Provide a succinct discussion of relevant background information to justify performing the proposed study.

Veteran suicide is an epidemic; from 2005-2016, suicide rates have risen 26% despite increased prevention efforts. Suicide prevention is VA's highest priority. Efforts to expand and develop innovative services are required to address this ever-growing problem. Thwarted belongingness and perceived burdensomeness are potent transdiagnostic social risk factors for suicide. Unfortunately, few interventions have directly targeted these constructs to reduce suicide risk. The overarching goal of this project is to refine and evaluate Caring Cards, an innovative peer-centered intervention that aims to reduce suicide risk by promoting social recovery among Veterans. Inspired by caring contacts for suicide prevention and the recovery model, Caring Cards employs a novel approach to social recovery by leveraging Veterans' lived experience with mental health conditions. In Caring Cards, Veterans compose messages of hope and unity by handmaking one-of-a-kind cards in outpatient groups. These cards are then sent to their anonymous peers who identified to be at elevated risk for suicide.

In a recent pilot study conducted by [name] and colleagues (IRB #H190032), preliminary data indicate Caring Cards is highly feasible and acceptable to both Veteran card makers and recipients. These data also suggest Caring Cards benefits both Veteran card makers and

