Optional Meet-Up Groups (card makers and recipients): All study participants will be invited to attend one or more monthly, 120-minute optional, unstructured meetup groups at the VASDHS facilitated by a therapist. A total of four meet-up groups will be offered throughout the study's duration. Again, if COVID-19 precautions are in effect and these groups cannot meet in person, they will be invited to meet via WebEx. Meet-up groups will begin with an introduction to the purpose of the group (i.e., the facilitator will explain that this is an opportunity for the card makers and recipients to meet one another) followed by a review of basic group rules (i.e., limits of confidentiality will be reviewed, group members will be informed that they are free to come and go as they please, meaning they can arrive later than the designated start time and leave earlier than the end time, and the facilitator will be available if anyone has any questions or concerns). The facilitator will remind meet-up group attendees that if they are having thoughts of suicide or homicide, they should speak directly to them. If group is conducted virtually, the Veteran may ask the facilitator to call them after the group has concluded. If suicide is reported, the group's facilitator will further assess their risk by completing a C-SSRS; if the Veteran's C-SSRS is positive, the facilitator will contact the PI for further risk assessment and Safety Planning.

Follow-up Assessments: All follow-up assessments will be collected in-person or via remote methods described above by the study coordinator.

Follow-up assessment battery includes: Beck Scale for Suicidal Ideation (BSS), C-SSRS "Since Last Contact," Interpersonal Needs Questionnaire (INQ-15), NIH Toolbox Adult Social Relationship Scales, and Intervention Satisfaction Questionnaire (developed by PI).

Card makers: Veterans are expected to participate in the Caring Cards groups for six months. Follow-up assessments will be collected within one month of the last group meeting. If a card maker drops out prior to the group's end date, follow-up will be collected within one month the last group meeting they attended. **Card recipients:** Follow-up assessments will be collected within one month after the delivery of the final card. If a card recipient drops out prior to this, follow-up will be collected within one month after the last card they received.

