Feasibility & Acceptability: Feasibility for card makers will be assessed by the proportion of enrolled Veterans who attend all scheduled Caring Cards groups. Feasibility for recipients will be assessed by the ratio of cards sent and received. For all participants, feasibility will be measured by the proportion of Veterans 1) referred for screening, 2) determined eligible, 3) enrolled /completed baseline, and 4) complete follow-up assessments. Feasibility of the optional meet-up groups will also be evaluated based on average attendance. Acceptability for all participants will be assessed by the Intervention Satisfaction Questionnaire, a measure that will be developed by the research team to assesses Veterans' satisfaction with their participation in the Caring Cards and meet-up groups (if attended), as well as asks for feedback about Caring Cards and assesses reasons for study dropout or non-attendance to meet-up groups.

Participant Compensation: Participants will be paid a total of \$120 to complete the baseline and follow-up assessment (\$60 each). No recruitment will take place year two. We would like to pay participants \$120 at baseline, or \$60 at each assessment (baseline and follow-up).

Fidelity: For groups, Caring Cards is a manualized intervention and the facilitator (trained by the PI) will run the groups. The PI will review audiotapes of treatment delivery using a fidelity rating scale, and feedback will be shared in weekly supervision. To assess fidelity for sending cards, quantity, timing, and receipt of the cards will be recorded by the study's research assistant. The study coordinator will monitor the accuracy of this record.

In our original protocol we were approved to use VA-approved audio recording devices to record the groups to ensure fidelity. Given that some groups are likely to take place via telehealth, we would like to amend our protocol to include recording groups via WebEx. VA WebEx has a recording features and for all telehealth groups, we propose to use this feature to record the sessions. The recordings of these WebEx groups will be stored via within the VA WebEx account used to facilitate the group. These recordings will be stored via password protection behind VA firewall and encrypted VA-specific WebEx account (i.e., veteransaffairs.webex.com). Only study personnel will have access to these recordings.

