27.4b1) Identify precisely where **non-sensitive** electronic records/data will be stored to include the full map drive, network location/server name, etc., and a brief description of what data/information is stored at each location.

Non-sensitive information, which is the standard letter that was includes with each card was stored on the PI's personal H Drive on her secure, VA desktop. See below for full map drive.

\\R01SDCHSM02.R01.MED.VA.GOV\Homedir\$\[name]\My Documents\Research\Caring Cards

27.4b2) Identify precisely where **VASI** electronic records/data will be stored to include the full map drive, network location/server name, etc., and a brief description of what data/information is stored at each location.

If no VASI is collected or recorded for this study, simply indicate that the “Study does not collect or record VASI”.

A database of VASI is stored on the S drive, CORE folder, behind the VA firewall. See below for full map drive. The database is an Excel document that is password protected and only the PI has the password. The document includes the following information: Veteran name, last 4 of SSN, mailing address, telephone number, presence of high-risk flag, if eligible to receive card, date cards are mailed, date of assessments, all survey questions and the participants' answers, information about attendance to Caring Cards groups, and optional meet-up groups.

R:\Psychology\CORE\Research\Caring Cards

27.4b3) Are any of the locations described in 27.4b outside of the VA Secure Network? *Note: this includes storage on a computer local hard drive.*

Yes No

27.4c) Record Retention - VHA requires compliance with Records Control Schedule (RCS-10) for retention of electronic and hard copy records. Following study closure, these temporary records must be retained for six years and then destroyed. Longer retention may be permitted if required by other Federal regulations or requirements. Will RCS-10 requirements be followed (i.e., 6-year retention)?

I will adhere to VHA Records Control Schedule-10 requirements
 I request an exception to RCS-10 requirements

Section 27.5 Additional Privacy or Information Security Details

Provide any other privacy or information security details here.

Section 27.6 Attestations

In the event of real or suspected breach of security, the Information Security Officer, Privacy Officer, VA Police (if appropriate), and the individual's supervisor will be notified within one hour of learning of the event.

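### Section 9 measures card-maker feasibility by perfect attendance, but the 70% criterion in Aim 1 is for average attendance

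*Protocol*

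**What the plan says.** Section 6, Aim 1, defines feasibility and acceptability through a list of benchmarks: "70% average group attendance, > 75% average satisfaction with group participation and card receipt, and 70% average follow-up response". The attendance item in that list is an average.

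Section 9, Feasibility & Acceptability, states how card-maker feasibility will be measured: "Feasibility for card makers will be assessed by the proportion of enrolled Veterans who attend all scheduled Caring Cards groups". It gives no threshold for this proportion and does not name average attendance for the card-making groups. Later in the same paragraph the optional meet-up groups are treated differently: "Feasibility of the optional meet-up groups will also be evaluated based on average attendance". That does agree with Aim 1, which sets 70% average attendance for the meet-ups as well.

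On the groups themselves, Section 9 says that "they will meet separately for 120 minutes once per week at the VASDHS for six months" and that "enrollment will be capped at 10 Veterans per group (a total of 30 card makers"). The number of sessions is not given.

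**The concern.** An average attendance rate counts sessions: how much of what was offered did people attend? The proportion who attend everything counts persons: how many had no absence at all? A person who attends all but one session adds nearly a full unit to the first and nothing to the second.

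Feasibility is in the study title and in Aim 1, and attendance is the first benchmark listed. As the text stands, the statistic with a threshold is missing from the Methods, and the statistic in the Methods has no threshold. An analyst who follows Section 9 will produce a number that cannot be judged against Aim 1. With two measures on paper, the choice of which to report as the feasibility result could be made after the attendance data are seen.

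**Working it through.** The protocol derives no figure here that could be reproduced; 70% is a set benchmark. The check is how far the two statistics can differ on the same data.

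**Inputs**
- Card makers: 30, in three groups of 10 (Section 9).
- Benchmark: 70% average attendance (Section 6, Aim 1).
- Sessions per card maker, K: not stated. Weekly for six months is taken as K = 24 to 26 (assumption).
- Within-person correlation of attendance, ρ: not stated, shown over a range (assumption).

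**Bounds that need no attendance model**

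Let S be the share who attend every session and M the mean of sessions attended divided by sessions scheduled.

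1. Each perfect attender contributes 1 to the average and everyone else contributes at least 0, so M ≥ S. At M = 70%, S is at most 70%, or 0.70 × 30 = 21 people. That ceiling is reached only if 21 attend everything and the other 9 attend nothing.
2. If all 30 miss exactly one session, M = (K − 1)/K = 23/24 = 95.8% or 25/26 = 96.2%, while S = 0%.

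**Expected S at exactly 70% average attendance**

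With independent sessions, S = 0.7^K. This gives 0.7^24 = 0.00019 and 0.7^26 = 0.00009, so about 0.02% and 0.01%.

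If attendance varies between people, a beta-binomial model with mean 0.70 gives S = B(a + K, b)/B(a, b), where a + b = (1 − ρ)/ρ, a = 0.7(a + b) and b = 0.3(a + b).

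| ρ (assumed) | S, K = 24 | S, K = 26 | Roughly, of 30 |
|---|---|---|---|
| 0 | 0.02% | 0.01% | 0 |
| 0.1 | 1.9% | 1.6% | 0 to 1 |
| 0.2 | 6.9% | 6.3% | 2 |
| 0.3 | 13.7% | 13.0% | 4 |
| 0.5 | 29.6% | 28.9% | 9 |
| 0.7 | 46.0% | 45.5% | 14 |

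**If the 70% were carried over to the Section 9 measure**

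The protocol does not say this. Under independence the attendance needed per session would be 0.7^(1/K) = 98.5% (K = 24) or 98.6% (K = 26).

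**Side point: how dropouts count in the average**

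Section 9, Follow-up Assessments, foresees early leavers ("If a card maker drops out prior to the group's end date"), but only to time their follow-up assessment. As an illustration with assumed figures, suppose 24 of 30 stay, 6 leave after session 6, and everyone attends 80% of sessions while enrolled.
- Sessions counted only up to exit: M = 80%.
- All scheduled sessions counted: each leaver attends 0.8 × 6 = 4.8 sessions. For K = 24, M = (24 × 0.80 + 6 × 4.8/24)/30 = (19.2 + 1.2)/30 = 68.0%. For K = 26, M = (19.2 + 6 × 4.8/26)/30 = 67.7%.

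The two conventions fall on opposite sides of 70%.

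**The case against.** The best defence is that a decision rule does exist. Aim 1 defines feasibility by its benchmarks, and Section 9 neither withdraws them nor sets a rival threshold. On this view Section 9 lists descriptive indicators, most of them without thresholds, and the only pass/fail attendance test is the average. The Section 9 phrase may also be loose drafting for attendance across all scheduled groups: near-zero perfect attendance over some 25 weekly sessions would be an odd success measure to intend. The consequences are limited too. This is a small single-arm pilot, attendance is one of several Aim 1 criteria, and both statistics can be computed from the same records.

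Part of this stands. Only Aim 1 yields a verdict, the 70% average is already in writing, which restrains a later choice, and no data are lost. But Section 9 states its proportion as the way card-maker feasibility will be assessed, takes enrolled persons as the unit, and never mentions the average for these groups. The loose-drafting reading is weak, because the same paragraph uses average attendance where it means it, for the meet-ups.

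It is also fair that the correlation table rests on assumed values and is not an estimate; the two bounds are enough to make the point. The dropout rule is the kind of detail often left to an analysis plan and would not be a finding alone.

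**Conclusion.** The concern holds. Section 6 and Section 9 name different statistics for one criterion, and no other part of the protocol reconciles them. The possible gap is very wide: about 96% average attendance alongside 0% perfect attendance, and a perfect-attendance share anywhere from 0% to 70% when the average sits exactly on its threshold. The 0–70% range follows from the definitions alone. The 96% figure needs only the assumed 24 to 26 sessions. The intermediate percentages also depend on the beta-binomial model and the assumed correlations.

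This should be fixed, but it does not threaten the trial: the data to compute the right statistic will exist, and no treatment comparison depends on it.

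**What to change.** In Section 9, Feasibility & Acceptability, replace the card-maker measure with the one that Aim 1 benchmarks: the mean, over all enrolled card makers, of sessions attended divided by sessions scheduled, compared with 70%. Report the share attending every session as a descriptive figure only.

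In the same edit it would help to say how dropouts count. Counting a leaver's remaining scheduled sessions as not attended is preferable, because it stops early exits from inflating the average. This is a secondary suggestion.

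The cost is one or two sentences. Section 27.4b2 shows that the study database already holds "information about attendance to Caring Cards groups, and optional meet-up groups", so nothing new has to be collected.
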